#### Figure 1: Study Flow Diagram

\*The end of study visit in the neurocognitive function study (R727-CL-1532) will correspond to visit 1 (day 1) of this study. \*\*Starting dose is 75 mg Q2W. The first LDL-C assessment is at week 8. At any time after week 8, the investigator will be responsible to manage the PRALUENT dose by either modifying from 75 mg Q2W to 150 mg Q2W, maintain the dose, modifying from 150 mg Q2W to 75 mg Q2W or discontinuing the treatment with PRALUENT at any time during the treatment period.

## 5.1.1. End of Study Definition

The end of study for this study is defined as the last visit of the last patient.

# 5.2. Planned Interim Analysis

No interim analysis is planned.

## 5.3. Study Committees

#### 5.3.1. Neurocognitive Events Review Committee

The neurocognitive events review committee is composed of recognized clinical experts in the field of cognition, independent from the sponsor and the investigators. This committee will be responsible for defining and validating, and classifying AEs of special interest possibly related to cognition impairment.

#### **Regeneron Pharmaceuticals, Inc.**

CONFIDENTIAL

Page 22 of 57

A charter and an operational manual will specify the procedures and criteria used for review of these events.

# 6. SELECTION, WITHDRAWAL, AND REPLACEMENT OF PATIENTS

# 6.1. Number of Patients Planned

No formal sample size was calculated for this study. The anticipated number of patients is based on the previously observed drop-out rate in the ODYSSEY program. The expected total number of patients is approximately 1600.

# 6.2. Study Population

The study population consists of patients with heFH or non-FH patients at high or very high cardiovascular risk. Patients must have had a history of coronary heart disease (CHD) without adequate control of their hypercholesterolemia with LDL-C  $\geq$ 70 mg/dL, or with LDL-C  $\geq$ 100 mg/dL with no history of CHD, and be on a maximally-tolerated dose of statin (unless they are statin-intolerant).

## 6.2.1. Inclusion Criteria

A patient must meet the following criteria to be eligible for inclusion in the study:

- 1. Patients having been randomized into the neurocognitive function study (R727-CL-1532) who completed treatment and the EOS visit with no premature or permanent discontinuation of study drug.
- 2. Willing and able to comply with clinic visits and study-related procedures
- 3. Provide signed informed consent

## 6.2.2. Exclusion Criteria

A patient who meets any of the following criteria will be excluded from the study:

- 1. Significant protocol deviation in the parent study (neurocognitive function study, R727-CL-1532) based on the investigator's or sponsor's judgment, such as noncompliance by the patient
- 2. Any patient who experienced an AE leading to permanent discontinuation from the neurocognitive function study, (R727-CL-1532).
- 3. Any new condition or worsening of an existing condition which, in the opinion of the investigator or per the PRALUENT local label, would make the patient unsuitable for enrollment or could interfere with the patient participating in or completing the OLE study
- 4. Known hypersensitivity to monoclonal antibody or any component of the drug product
- 5. Pregnant or breastfeeding women
- 6. Women of childbearing potential\* who are unwilling to practice highly effective contraception prior to the initial dose/start of the first treatment, during the study, and for

## CONFIDENTIAL

Page 23 of 57

at least 6 months after the last dose. Highly effective contraceptive measures include stable use of combined (estrogen and progestogen containing) hormonal contraception (oral, intravaginal, transdermal) or progestogen-only hormonal contraception (oral, injectable, implantable) associated with inhibition of ovulation initiated 2 or more menstrual cycles prior to screening; intrauterine device (IUD); intrauterine hormone-releasing system (IUS); bilateral tubal ligation; vasectomized partner; and or sexual abstinence\*\*†.

\*Postmenopausal women must be amenorrheic for at least 12 months in order not to be considered of childbearing potential. Pregnancy testing and contraception are not required for women with documented hysterectomy or tubal ligation.

\*\*Sexual abstinence is considered a highly effective method only if defined as refraining from heterosexual intercourse during the entire period of risk associated with the study treatments. The reliability of sexual abstinence needs to be evaluated in relation to the duration of the clinical trial and the preferred and usual lifestyle of the subject.

†Periodic abstinence (calendar, symptothermal, post-ovulation methods), withdrawal (coitus interruptus), spermicides only, and lactational amenorrhea method (LAM) are not acceptable methods of contraception. Female condom and male condom should not be used together.

# 6.3. Premature Withdrawal from the Study

A patient has the right to withdraw from the study at any time, for any reason, and without repercussion.

The investigator and/or sponsor have the right to withdraw a patient from the study if it is no longer in the interest of the patient to continue in the study, or if the patient's continuation in the study places the scientific outcome of the study at risk (eg, if a patient does not or cannot follow study procedures). An excessive rate of withdrawals would render the study uninterpretable; therefore, unnecessary withdrawal of patients should be avoided.

Patients who are withdrawn prematurely from the study will be asked to complete study assessments, as described in Section 8.1.2.

Rules for discontinuation of study treatment (permanent or temporary) are discussed in Section 7.3.2.

# 6.4. Replacement of Patients

Patients prematurely discontinued from the OLE study/study drug will not be replaced.

# 7. STUDY TREATMENTS

# 7.1. Investigational and Reference Treatments

Sterile PRALUENT drug product will be supplied at a concentration of 75 mg/mL and 150 mg/mL in histidine, pH 6.0, polysorbate 20, and sucrose, both as 1 mL volume in an auto-injector.

# 7.2. Background Treatments

Throughout the treatment period, patients should remain on stable, maximally-tolerated registered daily dose of statin received during the neurocognitive function study (R727-CL-1532), with or without other LMT. The statin dose should not be modified to adjust the degree of LDL-C lowering.

Background LMT should not be changed during the course of the study. However, if clinically necessary, background LMT may be adjusted at the investigator's discretion. Any adjustment will be documented in the CRF. For adjustments based on LDL-C values, simultaneous adjustments in PRALUENT dose and any LMT should be avoided.

For background LMT, including statins, sites must follow the national product label for the safety monitoring and management of patients.

No lipid profile will be performed until week 8, to avoid any unblinding of the neurocognitive function study.

As background treatment, the following classes of drugs are identified as non-investigational medicinal products:

- Concomitant LMT, including statins
- Cholesterol absorption inhibitors (ezetimibe)
- Bile acid-binding sequestrants (such as cholestyramine, colestipol, colesevelam)
- Nicotinic acid (niacin)
- Fenofibrate, fenofibric acid
- Omega-3 fatty acids

## 7.3. Dose Modification and Study Treatment Discontinuation Rules

#### 7.3.1. Dose Modification

Dose modification/reduction is allowed for an individual patient according to the following specifications:

• The starting dose of PRALUENT will be 75 mg administered SC Q2W. The dose may be modified to 150 mg administered SC Q2W, and can be maintained or modified from 150 mg Q2W to 75 mg Q2W.

#### 7.3.2. Study Drug Discontinuation

Patients who permanently discontinue from study drug will be asked to complete early termination study assessments, per Section 8.1.2.

#### 7.3.2.1. Reasons for Permanent Discontinuation of Study Drug

Study drug dosing will be permanently stopped in the event of:

- Pregnancy, intention for pregnancy, or no longer using effective contraceptive method of birth control (females only). All pregnancies will be followed to their outcome.
- Acute injection reaction of clinical concern
- SAE (or non-serious but severe in intensity) of hypersensitivity reaction considered related to study drug
- At patient request, ie, withdrawal of the consent for treatment
- If, in the investigator's opinion, continued administration of study drug would be detrimental to the patient's safety or well-being. Any abnormal laboratory value will be immediately rechecked for confirmation before making a decision of permanent discontinuation of study drug
- At the specific request of the sponsor

## 7.3.2.2. Reasons for Temporary Discontinuation of Study Drug

Temporary treatment discontinuation may be considered by the investigator because of suspected AEs. Reinitiating of treatment with the study drug will be done under close and appropriate clinical/and or laboratory monitoring once the investigator will have considered (according to his/her best medical judgement) that the responsibility of the study drug in the occurrence of the concerned event was unlikely, and if the selection criteria for the study are still met (see Sections 6.2.1 and 6.2.2).

For all temporary treatment discontinuations, duration should be recorded by the investigator in the appropriate screens of the CRF.

Treatment interruption is defined as 1 or more scheduled injections that are not administered to the patient as decided by the investigator.

## 7.4. Method of Treatment Assignment

This is an open-label study and every patient will receive PRALUENT. Treatment kit numbers will be allocated via interactive voice response system (IVRS)/interactive web response system (IWRS). Patients will keep the same identification number that they were allocated in the neurocognitive function study (R727-CL-1532) or a correspondence table will be set up between the neurocognitive function study (R727-CL-1532) and this study numbering.

From week 8, the investigator will manage the PRALUENT dose at his/her discretion based on LDL-C values obtained from the sample at the previous scheduled visit, by either modifying the dose from 75 mg Q2W to 150 mg Q2W, maintaining the PRALUENT dose, or discontinuing treatment with PRALUENT at any time during the treatment period. The statin dose should not be modified to adjust the degree of LDL-C lowering.

**Regeneron Pharmaceuticals, Inc.** 

An unscheduled kit dispensation visit may be scheduled at any time during the study after the week 12 visit if the investigator, based on lipid results or safety issues, decides to modify the dose of PRALUENT (see Section 8.1). In this instance, IVRS/IWRS will allocate a new treatment kit number and the new study drug kit will be dispensed to the patient. In specific cases, the new kit may be sent directly to the patient's home.

## 7.4.1. Blinding

This is an open-label, uncontrolled study; therefore, no blinding procedures will be implemented.

# 7.5. Treatment Logistics and Accountability

## 7.5.1. Packaging, Labeling, and Storage

Open-label study drug will display the product lot number on the label.

Study drug will be stored at the site at a temperature of 2°C to 8°C; storage instructions will be provided in the study manual.

## 7.5.2. Supply and Disposition of Treatments

Study drug will be shipped at a temperature of 2°C to 8°C to the investigator or designee at regular intervals or as needed during the study. At specified time points during the study (eg, interim site monitoring visits), at the site close-out visit, and following drug reconciliation and documentation by the site monitor, all opened and unopened study drug will be returned to the sponsor or designee.

## 7.5.3. Treatment Accountability

All drug accountability records must be kept current.

The investigator must be able to account for all opened and unopened study drug. These records should contain the dates, quantity, and study medication

- dispensed to each patient,
- returned from each patient (if applicable), and
- disposed of at the site or returned to the sponsor or designee

All accountability records must be made available for inspection by the sponsor and regulatory agency inspectors; photocopies must be provided to the sponsor at the conclusion of the study.

## 7.5.4. Treatment Compliance

Patients will complete a dosing log to document compliance with study drug administration. Measures taken to ensure and document study drug accountability and compliance are as follows:

- The investigator or designee will obtain, via IVRS/IWRS, the treatment kit number(s) and will dispense the treatment kit(s) to the patient.
- Accountability is to be verified during study drug kit re-supply visits only. The used and unused kit(s) should be brought to these visits for accountability purposes.
- All kits, including used and unused kits, are to be returned by the patient at the designated visit. An unused kit contains the unused auto-injector.

- All sharps containers should be returned to the site by the patient.
- The investigator/study coordinator will enter data in the appropriate CRF pages, according to data recorded in the treatment log form.
- The monitor will check the data consistency among CRF pages, treatment log form and returned unused kit(s).

All treatments kits will be retrieved by the sponsor. A detailed treatment log of the returned study drug will be established with the investigator or designee and countersigned by the investigator and the monitoring team.

All drug compliance records must be kept current and made available for inspection by the sponsor and regulatory agency inspectors.

## 7.6. Concomitant Medications

Any treatment administered from the time of informed consent to the final study visit will be considered concomitant medication. This includes medications that were started before the study and are ongoing during the study.

Concomitant medications should be kept to a minimum during the study. However, if considered necessary for the patient's welfare and unlikely to interfere with study drug, a stable dose, when possible, may be given at the discretion of the investigator.

Concomitant medications allowed during the study include:

#### Lipid Modifying Therapy

Throughout the treatment period, patients should stay on a stable maximally-tolerated registered daily dose of statin, with or without other LMT, received during the neurocognitive function study (R727-CL-1532).

Lipid modifying therapy, including statins, should not be changed during the course of the study. However, if clinically necessary, background LMT may be adjusted at the investigator's discretion. Any adjustment will be documented in the CRF.

#### **Contraception**

Women of childbearing potential must use an effective contraceptive method throughout the study treatment, and for at least 6 months after the last study drug injection.

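### The rules for continued dosing (Protocol 7.6) and permanent stop (7.3.2.1) ask only for effective contraception, while Exclusion 6 and, through it, the restart rule ask for highly effective contraception

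*Protocol*

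**What the plan says.** Four places in the protocol set a contraception standard for women of childbearing potential.

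- **Entry, Section 6.2.2, Exclusion 6.** A woman is excluded if she is "unwilling to practice highly effective contraception prior to the initial dose/start of the first treatment, during the study" and for at least 6 months after dosing ends. The term is given content: "Highly effective contraceptive measures include stable use of combined (estrogen and progestogen containing) hormonal contraception", followed by other named methods. A note to the criterion names methods that are not acceptable (periodic abstinence, withdrawal, spermicides alone, lactational amenorrhea).
- **Restart after a pause, Section 7.3.2.2.** Treatment may be resumed only "if the selection criteria for the study are still met (see Sections 6.2.1 and 6.2.2"), which brings in Exclusion 6.
- **Continued dosing, Section 7.6, Contraception.** "Women of childbearing potential must use an effective contraceptive method throughout the study treatment", with the same 6-month tail.
- **Permanent stop, Section 7.3.2.1.** "Study drug dosing will be permanently stopped in the event of" several listed reasons, one of which is a woman "no longer using effective contraceptive method of birth control".

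Sections 7.6 and 7.3.2.1 neither define the shorter term nor point to Section 6.2.2. No other part of the protocol says that the two terms mean the same thing.

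**The concern.** Exclusion 6 is applied at enrollment. Sections 7.6 and 7.3.2.1 are what a site consults later, when a woman already on treatment reports that she has changed method. Treatment is planned for approximately 192 weeks, so such changes are plausible. At that moment the two sections that govern her dosing give the weaker word and no list.

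Two consequences follow from the literal text. A site could keep dosing a woman on a method that does not meet Exclusion 6. And two women on the same method could be treated differently: one who paused for a suspected adverse event would have to meet Section 6.2.2 before restarting, while one who never paused would not. What is at stake is avoidable exposure of a pregnancy to study drug, not the statistical results.

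**Working it through.** No arithmetic applies; the plan gives no figure on this point. The check sets the four rules side by side.

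| Situation | Section | Standard stated | Defined there or by reference? |
|---|---|---|---|
| Entry | 6.2.2, Exclusion 6 | Highly effective | Yes: methods listed, unacceptable ones named |
| Restart after a pause | 7.3.2.2 | Highly effective, through 6.2.2 | Yes, by reference |
| Continued dosing | 7.6 | Effective | No |
| Permanent stop | 7.3.2.1 | Effective | No |

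**Step 1: does Exclusion 6 reach past entry?** In part. The period it names runs through the study and the 6 months after, so the intended standard is clear. Formally, though, it tests whether a woman is willing at enrollment. It does not say what the site must do if her method changes later.

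**Step 2: a test case.** Suppose a woman enters on combined hormonal contraception and later relies on a male condom alone. That method is not in the Exclusion 6 list. Nor is it among the methods named as unacceptable; the note says only that male and female condoms should not be used together.

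- Under 7.6, a site could accept the condom as effective, so dosing continues.
- Under 7.3.2.1, on the same reading, she has not stopped using an effective method, so no permanent stop is triggered.
- Under 7.3.2.2, if she pauses for a suspected adverse event, she must meet Section 6.2.2 again. On the listed methods she does not, so she cannot restart.

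The outcome depends on whether she happened to pause.

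**Step 3: how wide is the restart route?** Narrow. Section 7.3.2.2 opens with "Temporary treatment discontinuation may be considered by the investigator because of suspected AEs", so it is written for pauses related to adverse events. It would not pick up most women whose method changes.

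**Step 4: size.** The documents give neither the number of women of childbearing potential nor the frequency of method changes, so the number affected cannot be computed. SAP Section 1.1 records that the sponsor terminated the study on January 31, 2020, which limits any practical reach.

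The test case assumes that the Exclusion 6 list is meant to be complete. It is introduced by a word that could be read as giving examples, but the list is the only content the protocol gives to the stricter term.

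**The case against.** The strongest reply is that Section 7.6 is shorthand. It covers the same women, the same treatment period and the same 6-month tail as Exclusion 6, and the note on unacceptable methods is not limited to entry. A sensible investigator would read the two together. This stands as far as intent goes: the standard is not missing, and the wordings do not contradict each other, because a woman on a highly effective method satisfies both. It does not remove the gap, since the two operative on-treatment rules never refer to the defined term.

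It is also fair to say that the scenario is narrow and that other safeguards exist. Urine pregnancy tests are scheduled at every visit, pregnancy or intended pregnancy is itself a permanent-stop reason, pregnancies are reportable within 24 hours up to 180 days after the last dose, and the investigator may stop dosing on safety grounds. These limit the harm. However, the tests detect a pregnancy after it has begun, and from week 24 they are 24 weeks apart.

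A reader might go further and infer that Table 1 footnote 1, which treats any discontinuation as temporary at first, conflicts with the permanent stops in Section 7.3.2.1. The documents do not support that. The footnote makes resumption conditional on there being no safety concerns and has its own route for a permanent stop. Section 7.3.2.1 is mandatory in its wording and already lists "withdrawal of the consent for treatment". Section 6.3 separately gives the patient the right to withdraw, and gives the investigator and sponsor the right to withdraw a patient. A blanket exception in the footnote would also drop the useful prompt to explore resumption when a patient asks to stop.

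**Conclusion.** The point holds as a minor patient-safety inconsistency. The standard for continuing study drug and the trigger for stopping it are worded more weakly than the standard for entry and restart, and the weaker word is undefined. No endpoint, estimate or analysis is affected.

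A reader might infer that women were in fact dosed on inadequate contraception. The documents give no basis for that: they contain no count of method changes, and Exclusion 6 shows which standard was intended. The conclusion rests on a literal reading of Sections 7.6 and 7.3.2.1 and on treating the Exclusion 6 list as the meaning of the stricter term. Because the study has ended, the practical value lies mainly in correcting the text wherever it is reused.

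**What to change.** Two wording changes:

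- **Section 7.6, Contraception:** require *a highly effective contraceptive method (as defined in Section 6.2.2)*.
- **Section 7.3.2.1, first bullet:** replace the contraception trigger with *no longer using a highly effective contraceptive method (Section 6.2.2) and not returning to one*.

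The Section 7.6 change costs a few words. The Section 7.3.2.1 change tightens a stopping rule, so a few more women may have to stop study drug. Under Table 1 footnote 1 the early termination visit is then their last, which ends their scheduled follow-up, and Section 6.3 asks that unnecessary withdrawal be avoided. The clause on not returning to a qualifying method keeps that cost down, because a woman who resumes one need not be stopped permanently. Table 1 footnote 1 needs no change.

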#### 7.6.1. **Prohibited Medications**

PCSK9 inhibitors, other than PRALUENT, taken from the time of informed consent until the last study visit, are prohibited during the study.

#### 7.6.2. Permitted Medications

Concomitant medications should be kept to a minimum during the study. However, if these are considered necessary for the patient's welfare and are unlikely to interfere with the study drug, they may be given at the discretion of the investigator at a stable dose (when possible). Besides the specific information related to concomitant medications provided in this section, any other

concomitant medication(s) will be allowed and are required to be recorded in the CRF and source data.

# 8. STUDY SCHEDULE OF EVENTS AND PROCEDURES

# 8.1. Schedule of Events

Study assessments and procedures are presented by study period and visit in Table 1.

